APPENDIX 2 RECIST 1.1

1 **ASSESSMENT OF OVERALL TUMOR BURDEN AND MEASURABLE DISEASE**

To assess objective response or future progression, it is necessary to estimate the *overall tumor burden at baseline* and use this as a comparator for subsequent measurements. Measurable disease is defined by the presence of at least one measurable tumor lesion. When CT scans have slice thickness greater than 5 mm, the minimum size for a measurable lesion should be twice the slice thickness.

At baseline, tumor lesions/lymph nodes will be categorized measurable or non-measurable as follows:

1.1 **Measurable Lesions**

Measurable lesions must be accurately measured in at least one dimension (longest diameter in the plane of the measurement to be recorded) with a minimum size of:

- 10 mm by CT/MRI scan - (CT/MRI scan slice thickness no greater than 5 mm)
- 20 mm by chest x-ray
- *Malignant lymph nodes*: To be considered pathologically enlarged *and* measurable, a lymph node must be ≥ 15 mm in *short* axis when assessed by CT scan (CT scan slice thickness recommended to be no greater than 5 mm). At baseline and in follow-up, only the *short* axis will be measured and followed.

1.2 **Non-measurable Lesions**

- All other lesions, including small lesions (longest diameter < 10 mm or pathological lymph nodes with ≥ 10 to < 15 mm short axis), as well as truly non-measurable lesions.
- Lesions considered truly non-measurable include: leptomeningeal disease, ascites, pleural or pericardial effusion, inflammatory breast disease, lymphangitic involvement of skin or lung, abdominal masses/abdominal organomegaly identified by physical exam that is not measurable by reproducible imaging techniques.

1.3 **Special Considerations Regarding Lesion Measurability**

1.3.1 **Bone Lesions**

- Bone scan, PET scan or plain films are *not* considered adequate imaging techniques to measure bone lesions. However, these techniques can be used to confirm the presence or disappearance of bone lesions.

- Lytic bone lesions or mixed lytic-blastic lesions, with *identifiable soft tissue components*, that can be evaluated by cross sectional imaging techniques such as CT or MRI can be considered as measurable lesions if the *soft tissue component* meets the definition of measurability described above.
- Blastic bone lesions are non-measurable.

1.3.2 Cystic Lesions

- Lesions that meet the criteria for radiographically defined simple cysts should not be considered as malignant lesions (neither measurable nor non-measurable) since they are, by definition, simple cysts.
- ‘Cystic lesions’ thought to represent cystic metastases can be considered as measurable lesions, if they meet the definition of measurability described above. However, if non-cystic lesions are present in the same subject, these are preferred for selection as target lesions.

1.3.3 Lesions with Prior Local Treatment

Tumor lesions situated in a previously irradiated area, or in an area subjected to other loco-regional therapy, are usually not considered measurable unless there has been demonstrated progression in the lesion.

1.4 Specifications by Methods of Measurements

1.4.1 Measurement of Lesions

All measurements should be recorded in metric notation (mm). All baseline evaluations should be performed as close as possible to the treatment start and never more than 30 days before the beginning of the treatment.

1.4.2 Method of Assessment

The **same method of assessment and the same technique should be used** to characterize each identified and reported lesion at baseline and during follow-up. Imaging based evaluation should always be done rather than clinical examination unless the lesion(s) being followed cannot be imaged but are assessable by clinical exam.

1.4.2.1 CT/MRI Scan

CT/MRI is the best currently available and reproducible method to measure lesions selected for response assessment. Measurability of lesions on CT/MRI scan is based on the assumption that CT/MRI slice thickness is 5 mm or less. When CT scans have slice thickness greater than 5 mm, the minimum size for a measurable lesion should be twice the slice thickness.

1.4.2.2 Chest X-ray

Chest CT is preferred over chest X-ray, particularly when progression is an important endpoint, since CT is more sensitive than X-ray, particularly in identifying new lesions. However, lesions on chest X-ray may be considered measurable if they are clearly defined and surrounded by aerated lung.

1.4.2.3 Clinical Lesions

Clinical lesions will only be considered measurable when they are superficial and ≥ 10 mm diameter as assessed using calipers. For the case of skin lesions, documentation by color photography including a ruler to estimate the size of the lesion is suggested. As previously noted, when lesions can be evaluated by both clinical exam and imaging, imaging evaluation should be undertaken since it is more objective and may also be reviewed at the end of the study.

1.4.2.4 Ultrasound

Ultrasound is *not* useful in assessment of lesion size and should not be used as a method of measurement. If new lesions are identified by ultrasound in the course of the study, confirmation by CT or MRI is advised.

1.4.2.5 Endoscopy, Laparoscopy

The utilization of these techniques for objective tumor evaluation is *not* advised.

1.4.2.6 Tumor Markers

Tumor markers *alone* cannot be used to assess objective tumor response.

2 BASELINE DOCUMENTATION OF ‘TARGET’ AND ‘NON-TARGET’ LESIONS

2.1 Target Lesions

When more than one measurable lesion is present at baseline all lesions up to **a maximum of five lesions total (and a maximum of two lesions per organ) representative of all involved organs should be identified as *target lesions*** and will be recorded and measured at baseline.

Target lesions should be selected on the basis of their **size** (lesions with the longest diameter), be representative of all involved organs, and should lend themselves to ***reproducible repeated measurements***.

A ***sum of the diameters*** (longest for non-nodal lesions, short axis for nodal lesions) for all target lesions will be calculated and reported as the ***baseline sum diameters***. If lymph nodes are to be included in the sum, then as noted below, only the ***short*** axis is added into the sum. The baseline sum diameters will be used as reference to further characterize any objective tumor regression in the measurable dimension of the disease.

2.1.1 **Lymph Nodes**

Lymph nodes merit special mention since they are normal anatomical structures which may be visible by imaging even if not involved by tumor. Pathological nodes which are defined as measurable and may be identified as target lesions must meet the criterion of a **short axis of ≥ 15 mm by CT scan**. Only the *short* axis of these nodes will contribute to the baseline sum. Nodes that have a short axis < 10 mm are considered non-pathological and should not be recorded or followed.

2.2 **Non-target Lesions**

All other lesions (or sites of disease) including pathological lymph nodes should be identified as *non-target lesions* and should also be recorded at baseline. Measurements are not required and these lesions should be followed as ‘**present**’, ‘**absent**’, or in rare cases ‘**unequivocal progression**’. In addition, it is possible to record multiple non-target lesions involving the same organ as a single item on the case record form (e.g. ‘multiple enlarged pelvic lymph nodes’ or ‘multiple liver metastases’).

3 **TUMOR RESPONSE EVALUATION**

3.1 **Evaluation of Target Lesions**

Complete Response (CR): **Disappearance of all target lesions**. Any pathological lymph nodes (whether target or non-target) must have reduction in short axis to < 10 mm.

Partial Response (PR): At least a **30% decrease in the sum of diameters of target lesions**, taking as reference the baseline sum diameters.

Progressive Disease (PD): At least a **20% increase in the sum of diameters of target lesions, taking as reference the *smallest sum on study*** (this includes the baseline sum if that is the smallest on study). In addition to the relative increase of 20%, the sum must also demonstrate an **absolute increase of at least 5 mm**. (*Note*: the appearance of one or more new lesions is also considered progression).

Stable Disease (SD): Neither sufficient shrinkage to qualify for PR nor sufficient increase to qualify for PD, taking as reference the smallest sum diameters while on study.

3.1.1 **Special Notes on the Assessment of Target Lesions**

3.1.1.1 **Lymph Nodes**

Lymph nodes merit special mention since they are normal anatomical structures which may be visible by imaging even if not involved by tumor. Pathological nodes which are defined as measurable and may be identified as target lesions must meet the criterion of a **short axis of ≥ 15 mm by CT scan**. Only the *short* axis of these nodes will contribute to the baseline sum. Nodes that have a short axis < 10 mm are considered non-pathological and should not be recorded or followed.

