3.1.1.2 Target Lesions that Become ‘Too Small to Measure’

All lesions (nodal and non-nodal) recorded at baseline should have their actual measurements recorded at each subsequent evaluation, even when very small (e.g. 2 mm). If the radiologist is able to provide an actual measurement, that should be recorded, even if it is below 5 mm.

However, when such a lesion becomes difficult to assign an exact measure to then:

- If it is the opinion of the radiologist that the lesion has likely disappeared, the measurement should be recorded as 0 mm.
- If the lesion is believed to be present and is faintly seen but too small to measure, a default value of 5 mm should be assigned (note: in case of a lymph node believed to be present and faintly seen but too small to measure, a default value of 5 mm should be assigned in this circumstance as well). This default value is derived from the 5 mm CT slice thickness (but should not be changed with varying CT slice thickness).

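### Appendix 2's on-study notes say nodes under 10 mm are not to be recorded or followed, and its next subsection requires target nodes to be measured at every evaluation

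*Protocol*

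**What the plan says.** All references are to Protocol Appendix 2 unless stated.

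- **Baseline selection, section 2.1.1.** A node may be a target lesion only with a "short axis of ≥ 15 mm by CT scan". For small nodes the rule is "Nodes that have a short axis < 10 mm are considered non-pathological and should not be recorded or followed". At baseline this is a selection rule and causes no difficulty.
- **On-study assessment, section 3.1.1.1.** The same paragraph appears again word for word, within the section on response evaluation, under the title "Special Notes on the Assessment of Target Lesions".
- **On-study assessment, section 3.1.1.2.** "All lesions (nodal and non-nodal) recorded at baseline should have their actual measurements recorded at each subsequent evaluation, even when very small". It adds that "in case of a lymph node believed to be present and faintly seen but too small to measure, a default value of 5 mm" is assigned.
- **Complete response, section 3.1.** Any pathological node, target or not, "must have reduction in short axis to < 10 mm".
- **Partial response and progression, section 3.1.** PR is a "30% decrease in the sum of diameters of target lesions" relative to baseline. PD is a "20% increase in the sum of diameters of target lesions, taking as reference the" smallest sum on study, together with an absolute rise of at least 5 mm.
- **Missing measurements and confirmation, sections 4.1.1 and 4.1.2.** A time point with only some lesions measured is NE, unless a convincing case is made that the missing lesion would not alter the response. CR and PR must be confirmed at least 4 weeks later.

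Protocol section 5.4.2 bases PFS and ORR, the key secondary endpoints, on investigator assessment by RECIST 1.1. Section 4.5.1.1 sends investigators to Appendix 2 for the criteria.

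**The concern.** Take a target node of 16 mm at baseline that measures 9 mm on study. Section 3.1.1.1, read where it stands, says to stop recording it. Section 3.1.1.2 says to record 9 mm. No sentence limits the first to baseline or gives either precedence.

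The choice changes the sum of diameters, from which PR and PD are called. Those calls determine investigator-assessed PFS, ORR and DOR in an open-label trial, and the protocol describes no central reading of scans. The PFS sensitivity analyses in SAP section 7.5.2.2 vary strata, subsequent therapy, missed assessments and palliative radiotherapy; none touches lesion measurement. A measurement that was never recorded could not be put back into the sum at analysis.

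**Working it through.** The plan states no figure on this point, so there is none to reproduce. The check compares the texts and then applies Appendix 2's own thresholds to the same lesions under each reading.

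**Texts.** The CR rule fits only 3.1.1.2. CR must be confirmed at a later time point, so a node that has fallen below 10 mm still has to be looked at. The 5 mm default for a faint node likewise makes no sense if nodes below 10 mm are dropped.

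**Arithmetic.** The lesion sizes are illustrative assumptions; the thresholds are from section 3.1. *Actual* keeps the node's true size in the sum (3.1.1.2). *Dropped* counts a node below 10 mm as 0 mm and counts it again from 10 mm. Sizes are node + other target lesions, in mm, at baseline, scan 1 and scan 2.

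| Case | Rule | Sums | Scan 1 vs baseline | Scan 2 vs smallest sum |
|---|---|---|---|---|
| A: 16+40, 9+38, 10+38 | Actual | 56, 47, 48 | −16.1%: SD | +1 mm, +2.1%: SD |
| | Dropped | 56, 38, 48 | −32.1%: PR | +10 mm, +26.3%: PD |
| B: 16+30, 9+28, 9+34 | Actual | 46, 37, 43 | −19.6%: SD | +6 mm, +16.2%: SD |
| | Dropped | 46, 28, 34 | −39.1%: PR | +6 mm, +21.4%: PD |
| C: 15+14, 3+10, 9+10 | Actual | 29, 13, 19 | −55.2%: PR | +6 mm, +46.2%: PD |
| | Dropped | 29, 10, 10 | −65.5%: PR | 0 mm, 0%: no PD |

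- **Case A** is a false PD caused by re-entry: a 1 mm change in the node becomes a 10 mm change in the sum.
- **Case B** is a false PD without re-entry: the node stays at 9 mm, and the smaller denominator turns +16.2% into +21.4%.
- **Case C** is a missed PD: the node regrows from 3 to 9 mm and the sum does not register it.

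**When re-entry triggers PD.** With the other target lesions stable at S mm, the dropped sum goes from S to S + 10. The 5 mm minimum is always met. The relative rule needs 10/S ≥ 0.20, so S ≤ 50 mm. Check: 50 to 60 is +20.0% (PD); 51 to 61 is +19.6% (not PD).

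**What reaches ORR.** In case A the apparent PR is followed by PD. Under Table 2 in section 4.2 the best response is then SD if the minimum duration is met, otherwise PD, so nothing is added to ORR. If scan 2 instead repeats 9+38, the dropped sums are 56, 38, 38: −32.1% twice, against a true −16.1% twice. At the 6-week scan interval that would be a confirmed false PR.

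**If the node is treated as missing rather than 0 mm.** Section 4.1.1 can make the time point NE. Under Protocol section 8.3.2.1 a subject without an event is censored at the last evaluable assessment, so an NE scan can move that date earlier.

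**The case against.** The strongest reply is that 3.1.1.1 is plainly a baseline paragraph. It speaks of nodes that may be chosen as targets and of the baseline sum, it copies 2.1.1, and the explicit on-study rule follows at once. A careful site would read it so and measure the node. That is fair: harm arises only where a site applies the sentence on study. But the paragraph's placement invites that use, and nothing rules it out.

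The reply also limits the consequences, and these limits stand:

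- Appendix 2 does not say that an unrecorded node counts as 0 mm. Section 3.1.1.2 gives 0 mm only to a lesion thought to have disappeared, and section 4.1.1 points to NE.
- The 9-to-10 mm jump needs a site that stops recording the node and later re-enters it, a hybrid that no text prescribes. Case B does not need re-entry.
- Section 4.1.2 asks for equivocal progression to be verified, which may catch some false calls, although nothing ensures that a site would regard such a case as equivocal.

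A reader might infer that the appendix will produce false progressions and false responses at some appreciable rate, or that it favours one arm. The documents support neither. They give no frequency of nodal target lesions, the errors run in both directions, and both arms use the same appendix. Progression has different treatment consequences by arm (Protocol sections 3.5 and 4.5.4), but PFS is dated at initial progression in either case.

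**Conclusion.** Section 3.1.1.1 is wrong as written. It conflicts with 3.1.1.2 and with the CR rule, and should be corrected.

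The effect depends on a site applying it on study. If the dropped node is scored as 0 mm, a false PR, a false PD or a missed PD can follow; if it is treated as missing, NE can. The re-entry form of false PD also requires the node to be counted again at 10 mm, with the other target lesions stable at 50 mm or less.

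Investigator-assessed PFS is affected. ORR and DOR are affected only where the response is confirmed. OS, the primary endpoint, is unaffected, and PFS and ORR are formally tested only after OS succeeds (Protocol section 8.4.2). The cases above show that the errors can occur, not how often; the size of the effect on PFS or ORR cannot be computed from the documents.

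**What to change.** Replace the last sentence of Appendix 2 section 3.1.1.1 with:

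> Nodes chosen as target lesions at baseline keep their actual short-axis measurement in the sum of diameters at every assessment, even when < 10 mm (see 3.1.1.2); the < 10 mm exclusion applies only to the selection of nodes at baseline (see 2.1.1).

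Leave the CR rule unchanged. This adds no new criterion; it confines a baseline rule to baseline. The cost is one sentence and a reminder to sites, with no new scans or data fields.

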3.1.1.2 Target Lesions that Become ‘Too Small to Measure’

All lesions (nodal and non-nodal) recorded at baseline should have their actual measurements recorded at each subsequent evaluation, even when very small (e.g. 2 mm). If the radiologist is able to provide an actual measurement, that should be recorded, even if it is below 5 mm.

However, when such a lesion becomes difficult to assign an exact measure to then:

- If it is the opinion of the radiologist that the lesion has likely disappeared, the measurement should be recorded as 0 mm.
- If the lesion is believed to be present and is faintly seen but too small to measure, a default value of 5 mm should be assigned (note: in case of a lymph node believed to be present and faintly seen but too small to measure, a default value of 5 mm should be assigned in this circumstance as well). This default value is derived from the 5 mm CT slice thickness (but should not be changed with varying CT slice thickness).

3.1.1.3 Target Lesions that Split or Coalesce on Treatment

- When non-nodal lesions ‘fragment’, the longest diameters of the fragmented portions should be added together to calculate the target lesion sum.
- As lesions coalesce, a plane between them may be maintained that would aid in obtaining maximal diameter measurements of each individual lesion. If the lesions have truly coalesced such that they are no longer separable, the vector of the longest diameter in this instance should be the maximal longest diameter for the ‘coalesced lesion’.

3.2 Evaluation of Non-target Lesions

While some non-target lesions may actually be measurable, they need not be measured and instead should be assessed only qualitatively at the time points specified in the protocol.

Complete Response (CR): Disappearance of all non-target lesions and normalization of tumor marker level. All lymph nodes must be non-pathological in size (< 10 mm short axis).

Non-CR/Non-PD: Persistence of one or more non-target lesion(s) and/or maintenance of tumor marker level above the normal limits.

Progressive Disease (PD): *Unequivocal progression* of existing non-target lesions. (*Note*: the appearance of one or more new lesions is also considered progression).

3.2.1 Special Notes on Assessment of Non-target Lesions

The concept of progression of non-target disease requires additional explanation as follows:

3.2.1.1 When the Subject Also Has Measurable Disease

- To achieve ‘unequivocal progression’ on the basis of the non-target disease, there must be an overall level of substantial worsening in non-target disease such that, even in presence of SD or PR in target disease, the overall tumor burden has increased sufficiently to merit discontinuation of therapy.
- A modest ‘increase’ in the size of one or more non-target lesions is usually not sufficient to qualify for unequivocal progression status.

3.2.1.2 When the Subject Has Only Non-measurable Disease

- To achieve ‘unequivocal progression’ on the basis of the non-target disease, there must be an overall level of substantial worsening such that the overall tumor burden has increased sufficiently to merit discontinuation of therapy.
- A modest ‘increase’ in the size of one or more non-target lesions is usually not sufficient to qualify for unequivocal progression status.
- Because worsening in non-target disease cannot be easily quantified (by definition: if all lesions are non-measurable) a useful test that can be applied when assessing subjects for unequivocal progression is to consider if the increase in overall disease burden based on the change in non-measurable disease is comparable in magnitude to the increase that would be required to declare PD for measurable disease: i.e. an increase in tumor burden representing an additional 73% increase in ‘volume’ (which is equivalent to a 20% increase diameter in a measurable lesion). Examples include an increase in a pleural effusion from ‘trace’ to ‘large’, an increase in lymphangitic disease from localized to widespread, or may be described in protocols as ‘sufficient to require a change in therapy’.
- If ‘unequivocal progression’ is seen, the subject should be considered to have had overall PD at that point.

3.2.1.3 Tumor Markers

Tumor markers *alone* cannot be used to assess objective tumor responses. If markers are initially above the upper normal limit, however, they must normalize in order for a subject to be considered as having attained a complete response.

3.3 New Lesions

The appearance of new malignant lesions denotes disease progression. The finding of a new lesion should be unequivocal: i.e. not attributable to differences in scanning technique, change in imaging modality or findings thought to represent something other than tumor (for example, some ‘new’ bone lesions may be simply healing or flare of pre-existing lesions). This is particularly important when the subject’s baseline lesions show partial or complete response. For example, necrosis of a liver lesion may be reported on a CT scan report as a ‘new’ cystic lesion, which it is not.

A lesion identified on a follow-up study in an anatomical location that was *not* scanned at baseline is considered a new lesion and will indicate disease progression. An example of this is the subject who has visceral disease at baseline and while on study has a CT or MRI brain scan ordered which reveals metastases. The subject’s brain metastases are considered to be evidence of PD even if he/she did not have brain imaging at baseline.

If a new lesion is equivocal, for example because of its small size, continued therapy and follow-up evaluation will clarify if it represents truly new disease. *If repeat scans confirm there is definitely a new lesion, then progression should be declared using the date of the initial scan.*

3.3.1 FDG-PET Evaluation

While FDG-PET response assessments need additional study, it is sometimes reasonable to incorporate the use of the qualitative assessment of FDG-PET scanning to complement CT scanning in assessment of progression (particularly possible ‘new’ disease). New lesions on the basis of FDG-PET imaging can be identified according to the following algorithm:

- Negative FDG-PET at baseline, with a positive FDG-PET at follow-up is a sign of PD based on a new lesion.
- No FDG-PET at baseline and a positive FDG-PET at follow-up:
 - If the positive FDG-PET at follow-up corresponds to a new site of disease confirmed by CT, this is PD.
 - If the positive FDG-PET at follow-up is not confirmed as a new site of disease on CT, additional follow-up CT scans are needed to determine if there is truly progression occurring at that site (if so, the date of PD will be the date of the initial positive FDG-PET scan).
 - If the positive FDG-PET at follow-up corresponds to a pre-existing site of disease on CT that is not progressing on the basis of the anatomic images, this is not PD.

